##### **a. Initial Visit (Visit 1):**

1. The research staff will screen the patients' medical chart for inclusion and exclusion criteria (current CWC patients only).
2. The informed consent will be presented to the patient.
  - Confirmation of the study eligibility including the inclusion and exclusion criteria will be reviewed with the patient; Subjects who self-refer from outside of the IU system will be asked to sign a release of information form so records can be requested &

reviewed for inclusion/ exclusion criteria.

An ankle brachial index will be completed for subjects with below the knee wounds if not already completed per standard of care since wound onset to confirm study eligibility. Those with an ABI < 0.7 or > 1.2 will be excluded and no further study activities will be completed. These subjects will not be enrolled.

3. Included in this initial (baseline) visit will be:
  - Randomization into one of the 2 study groups per Randomization plan
  - Medical history review
  - Concomitant medication review
  - Wound history review (onset, location, etiology, size, infection status, previous treatments)
  - Digital imaging of ulcer input to Wound Matrix™
    - The digital images will be input into a secure web based wound management program, Wound Matrix™ (Wound Matrix, Inc., Chadds Ford, PA, USA) that will be used for planimetric analysis of wound size.
  - Patient will be asked to complete the quality of life questionnaire (SF-36)
  - Point-of-care testing Hemoglobin A1c will be obtained for all subjects who have not had one completed as SoC within 90 days prior to this visit
4. Patients will also be provided with teaching regarding diabetes, footwear, and wound care.
5. Patients will be given a diary (see example at the end) to log their treatment

**b. 4, 8, 12 Week Visit (+/- 2 weeks):** Subjects will be asked to return to the CWC to complete repeat digital imaging of the ulcer. For those who are receiving wound care at the CWC, as much as possible, study visits will be scheduled in conjunction with regularly scheduled wound care appointments. Additionally, for those randomized to the topical oxygen treatment group, all follow-up visits will be calculated from the first day of topical oxygen therapy. The following will be completed during the study visit:

- Digital imaging of the ulcer to measure the response to therapy
- Any wound or health complications will be noted
- Medication review
- Collection of previous diary
- Disbursement of new diary

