**Table-1: Study Timeline**

Week(s)	0 (Visit 1)	1-3	4 (Visit 2) (+/-2 weeks)	5-7	8 (Visit 3) (+/-2 weeks)	9-11	12 (Visit 4) (+/-2 weeks)	13-15	16 (Visit 5) (+/-2 weeks)
Study Visit	✓		✓		✓		✓		✓
Digital Imaging	✓		✓		✓		✓		✓
Topical oxygen or SoC treatment administered at home	✓	✓	✓	✓	✓	✓	✓	✓	✓

**Study Population:** 40 chronic wound patients with diabetes will be recruited based on study inclusion and exclusion criteria by the research personnel. Patients will be randomized into one of the 2 patient groups: the topical oxygen group and the other half randomized into the comparison group.

A proportionate stratified random permuted block design will be used to generate random assignments to the two groups. The stratification will be based on the proportion of patients expected to be seen at a wound center with Wagner grade 1, 2, or 3. This method will ensure balance across the groups and strata and will also account for the difference in the severity over the course of the study period. The biostatistician at the Center for Outcomes Research in Surgery will prepare the master randomization assignment list. The clinical research coordinator will administer randomization using REDCap.

**Blinding.** This is an open label trial. To reduce bias, the personnel involved in evaluating study outcomes will be blinded to treatment group. The standard of care will be provided by their providers at CWC as part of their routine wound care and will not be blinded to treatment group.

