**c. At Home Treatments (4 consecutive days per week, treatment group only):**

1. A trained, approved study personnel will first attend the subjects' home

or extended care facility to provide the supplies, instruct and give support on how to use the TO device (performed solely for research purposes only)

- The approved personnel will teach the subject how to use the TO device and instruct the subject to complete this treatment 4 consecutive days a week, followed by 3 days of no treatment.
- The treatment will begin with the study personnel during the first home care (on site) visit:
  - The 90 minute therapy includes the removal of the ulcer dressing, the ulcer is cleansed/ moistened and the extremity is inserted into an FDA cleared single use oxygen delivery device (GWR Medical, Inc. Chadds Ford, PA).
  - If necessary, a band around the wound is prepared for fixation of the Topical Oxygen device by shaving the limb circumferentially over approximately a 10cm band (done at initial treatment and as needed subsequently).
  - After the 90 minutes, the single use device will be removed and disposed of.
    - Wounds will be treated with standard care at the physician's discretion and diabetic foot ulcers (DFUs) will be administered with a standardized offloading boot to distribute pressure across the entire surface of the foot, specifically removing pressure from the ulcer site per SoC (a non-antimicrobial boot).

2. Trained study personnel will be assigned for the subject, who will receive at home support for the treatment. The study personnel will make weekly phone calls to the subject to check on progress with TO therapy; personnel may go to the subject's home/ care facility on as as-needed basis if the subject is having difficulty with the treatment.
3. Subjects will be given a data collection log (diary) to document the date, time and that the treatment was completed. This will be checked at each study visit and will be collected at their next follow-up visit for compliance.
4. Treatments will continue until the ulcer has closed, an amputation (above or below knee) has been performed, the ulcer's healing has stalled (defined that the size of the wound is unchanged or increased in size in the past 2 visits) or 16 weeks of therapy has been completed.

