d. **SoC group only-** Patients will receive Standard of Care for their wound per the study physician's discretion. There will be no at home treatments for this study population but they will be asked to return for follow-up visits at 4, 8, 12, and 16 weeks following their baseline visit.

1. Subjects will be given a data collection log (diary) to document information about the SoC including wound dressing intact, offloading boot being used (for DFU's), the date, and the subject's initials. This will be checked at each study visit and will be collected at their next follow-up visit for compliance.
2. SoC will continue until the ulcer has closed, an amputation (above or below knee) has been performed, or the ulcer's healing has stalled (defined that the size of the wound is unchanged or increased in size in the past 2 visits).

All wounds for both groups will be treated with standard care and will be administered with a standardized offloading boot that distributes the pressure across the entire surface of the foot, specifically removing pressure from the ulcer site will be utilized (a non-antimicrobial boot). Offloading boots are standard of care for these wounds and will not be provided by the study.

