#### **Week 16 (FSV) (+/- 2 weeks)/ Follow-up:**

Once the patient's ulcer has completely healed or the 16 weeks of treatment ends, the patient will return for their final study visit.

- If complete healing is achieved in less than 16 weeks, a follow-up visit will be scheduled at 16 weeks after enrollment.
  - Patients will be instructed to contact the study Physician should the ulcer recur.
  - The initially assigned oxygen treatments will be stopped at this time.
- Digital imaging of the ulcer to measure the response to therapy
- Quality of life questionnaire (SF-36) will be administered to all patients at 16 weeks.
- If the wound has not healed in 16 weeks, the wound is assessed as to its recent response to treatment.
  - Wounds, which have decreased less than 10% in wound surface area during the preceding 4 weeks, are designated as "Quiescent". Quiescent wounds are considered to be non-responders.

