#### **STUDY ASSESSMENTS AND PROCEDURES**

- a. **Wound Healing rates.** Wound healing rates will be determined from wound area measurement at baseline vs final visit using wound photography and Wound Matrix. Wound Matrix will be used to capture wound image, instantly upload wound images and obtain measurement of wound area data elements at the point of care. Measurement should be performed after debridement if there is one as a part of SoC. Wound matrix is a digital wound measurement

system that utilizes tablet/smartphone camera for taking a digital image of the wound in presence of a standard Ruler for size calibration. The image is automatically tracked and measured. The software tracks the outer perimeters of the wounds using a proprietary algorithm.

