## Statistical analysis.

Univariate analysis will be done using frequencies, mean (SD), median (IQR) to describe the patient cohort. Cumulative incidence of wound healing rates 16 weeks post treatment with 95% confidence interval around the risk estimate will be computed for the two groups (SoC and TO+SoC). Bivariate logistic regression will be used to report the odds of wound healing among those with TO+SoC compared to SoC only. Bivariate analysis to compare secondary outcomes between the groups will be done using Chi-square or Fisher's exact tests for categorical variables and t-tests or Mann-Whitney tests for continuous variables (e.g. QoL ratings from SF-36, costs).

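### The two arms' follow-up clocks start at different points (first oxygen versus the baseline visit), so any delay in starting oxygen gives unhealed TO wounds extra time to close

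*Combined protocol and SAP*

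**What the plan says.** All references are to the combined protocol and SAP.

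- **Shared start.** Under Study Procedure, a. Initial Visit, randomization and baseline imaging are part of Visit 1 for everyone.
- **TO clock.** Under b. 4, 8, 12 Week Visit: "for those randomized to the topical oxygen treatment group, all follow-up visits will be calculated from the first day of topical oxygen therapy".
- **SoC clock.** Under d. SoC group only: "they will be asked to return for follow-up visits at 4, 8, 12, and 16 weeks following their baseline visit".
- **Start of oxygen.** Under c. At Home Treatments: "The treatment will begin with the study personnel during the first home care (on site) visit". No maximum gap after Visit 1 is given, and no second baseline image at first oxygen. In Table 1, the row "Topical oxygen or SoC treatment administered at home" is ticked in the Week 0 column.
- **Final visit.** The Week 16 section says: "Once the patient's ulcer has completely healed or the 16 weeks of treatment ends, the patient will return for their final study visit". For wounds that heal early it says: "a follow-up visit will be scheduled at 16 weeks after enrollment", without distinguishing the arms.
- **Outcome and analysis.** Study Assessments, a. Wound Healing rates: "Wound healing rates will be determined from wound area measurement at baseline vs final visit using wound photography and Wound Matrix". Statistical analysis: "Cumulative incidence of wound healing rates 16 weeks post treatment with 95% confidence interval around the risk estimate will be computed" for the two groups, followed by a logistic regression with treatment as the only predictor.

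**The concern.** Both arms share one baseline image but have two time origins. A TO subject who first receives oxygen some days after Visit 1 has the final image that many days later, measured from randomization, than an SoC subject. Chronic wounds can close under standard care alone. Closures during the added days therefore count for TO, with no matching days in SoC. Randomization does not remove this, because the shift is built into one arm's schedule.

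The outcome wording does not settle the matter, since sixteen weeks after treatment names no origin common to both arms. The Week 16 section adds a third anchor, enrollment, for subjects who heal early. For the TO arm this conflicts with the rule that all follow-up visits run from first oxygen.

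What is at stake is the estimate more than the test. The Objective says that the pilot is meant to supply data for sizing a larger trial, so an arm-dependent shift in the healing rate would be carried forward.

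**Working it through.** **Inputs from the documents (Sample size):** 20 per arm; success 50% (TO+SoC) against 10% (SoC); one-sided Fisher's exact test at 0.05; at least 80% power claimed.

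**Plan's own figure.** Enumerating all 21 × 21 outcomes gives exact power of 83.7%, so the claim of at least 80% is met. This point does not alter it.

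**Assumptions, not in the documents.** The lag *d* is 1, 2 or 4 weeks. Oxygen has no effect. Every unhealed TO wound is observed for 16 + *d* weeks and every SoC wound for 16. The hazard of closure is constant (Weibull shape *k* = 1), with *k* = 0.5 (falling) and *k* = 2 (rising) as sensitivity checks.

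**Formula.** With SoC closure probability p = 0.10, H = −ln(1 − 0.10) = 0.1054. The TO probability is q = 1 − exp(−H × ((16 + d)/16)^k).

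Worked case, d = 2, k = 1: q = 1 − exp(−0.1054 × 1.125) = 1 − exp(−0.1185) = 0.1118, a spurious gain of 1.2 points.

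| Lag | k = 0.5 | k = 1 | k = 2 |
|---|---|---|---|
| 1 week | +0.3 | +0.6 | +1.2 |
| 2 weeks | +0.6 | +1.2 | +2.5 |
| 4 weeks | +1.1 | +2.3 | +5.2 |

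(percentage points, SoC 10%)

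For k = 1 the odds ratios are 1.07, 1.13 and 1.27 where the truth is 1.

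**Against sampling error.** SE = √(p(1 − p)/20 + q(1 − q)/20), which is 0.096 to 0.100 for k = 1. The bias is 0.06, 0.12 or 0.24 of a standard error.

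**Against the test.** At 10% SoC with no effect, one-sided Fisher rejection is 0.8% with no lag and 1.1%, 1.3% or 2.0% with the three lags (k = 1). Over the three shapes it reaches at most 4.3%, still below the nominal 5%.

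**Against sizing.** Take a 2-week lag at the SoC hazard, then 16 weeks on oxygen with 50% closure. The weekly hazard is 0.1054/16 = 0.00659, so observed TO = 1 − 0.50 × exp(−0.00659 × 2) = 0.5065. The pooled-variance two-proportion formula (two-sided 5%, 80% power) goes from 20 to 19 per arm.

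**If SoC healing is higher.** At an illustrative 30% (not in the documents), the constant-hazard bias is +1.5, +3.1 or +6.0 points, and Fisher rejection is 3.4%, 4.2% or 6.2% against 2.7% with no lag.

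**The case against.** The strongest reply is that the documents show no lag. Table 1 puts treatment at Week 0, and the requirement for an on-site start does not say that it falls after Visit 1. This stands as far as it goes: the bias is conditional. But oxygen needs its own home or care-facility visit with supplies and training, nothing caps the gap, and a separate TO clock makes a difference only when the two dates differ.

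A second reply is that timing from first oxygen lets every TO subject complete the 16-week course in the Study design. That is a reasonable aim for a feasibility pilot. It does not explain why closures between Visit 1 and first oxygen should count for TO without equal time in SoC.

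The visit window of two weeks either side does not cure the problem, because it is centred on a different date in each arm.

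Three stronger readings are tempting but unsupported:

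- **That the shift always favours TO.** This holds for healed/not healed. Study Assessments also derives healing from wound area, and the protocol allows for wounds that are unchanged or growing, so on an area scale extra weeks could go either way. Treatment may also end early for stalled healing or amputation, and the timing of those subjects' final visit is not clear. Not every unhealed TO wound need gain the full lag.
- **That it would badly undersize the next trial.** At the plan's own rates the change is one subject per arm. A fall such as 199 to 168 per arm arises only if the true TO rate is taken as 20%, which the documents do not give.
- **That the test is invalid.** At the planned 10% SoC rate it is not, in any scenario above. Fisher's test is named only for the sample size and healing is analysed by logistic regression, so the rejection rates are only indicative.

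**Conclusion.** The mismatch of anchors is in the text and needs reconciling whatever the lag. The bias that follows is conditional on oxygen starting after Visit 1, and applies to unhealed TO wounds on the binary closure outcome. At the plan's 10% SoC rate it is about 0.6 to 2.3 points for lags of 1 to 4 weeks under a constant hazard, and 0.3 to 5.2 points across the three hazard shapes. The lags and shapes are assumptions. For lags of 1 or 2 weeks under a constant hazard, that is about an eighth of a standard error or less. The enrollment anchor for early healers is an inconsistency, not a further source of bias. Severity: minor.

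**What to change.** 1. Date the primary wound image, healed or not, at 16 weeks after randomization in both arms with the same window. Define the primary outcome in the Objective, Study Assessments and Statistical analysis as healing by that date.
2. Reconcile the visit anchors in Table 1, the 4, 8, 12 Week Visit section, the SoC group section and the Week 16 section. Leave the treatment schedule as it is. An end-of-therapy image may stay as a secondary measure.
3. Report, by arm, the days from randomization to the final image and, for TO, to first oxygen. The treatment diary and image dates should largely supply these.
4. For subjects already followed on the present clock, add one sensitivity analysis adjusting for actual time from baseline to final image. Treat it as a rough check, since elapsed time is partly tied to arm. The Objective lists 11 subjects already enrolled at the first site; whether the same anchors applied to them is not stated.

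Do not use the last image on or before day 112 (16 × 7) as the check. With a 1-week lag, TO images fall at weeks 5, 9, 13 and 17 from randomization, so TO is cut back to week 13 while SoC keeps week 16. Under the constant-hazard model this gives (1 − 0.9^(13/16)) − 0.10 = −1.8 points, larger than the +0.6 being examined.

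**Cost.** An amendment to wording. Some TO subjects will have had slightly less than 16 weeks of oxygen at the primary image, by the length of their lag. Keeping a separate end-of-therapy image adds at most one visit for each of about 20 TO subjects (20 × $25 = $500 at most) and would require changing the five-visit limit in the Payment section.

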**c. At Home Treatments (4 consecutive days per week, treatment group only):**

1. A trained, approved study personnel will first attend the subjects' home

or extended care facility to provide the supplies, instruct and give support on how to use the TO device (performed solely for research purposes only)

- The approved personnel will teach the subject how to use the TO device and instruct the subject to complete this treatment 4 consecutive days a week, followed by 3 days of no treatment.
- The treatment will begin with the study personnel during the first home care (on site) visit:
  - The 90 minute therapy includes the removal of the ulcer dressing, the ulcer is cleansed/ moistened and the extremity is inserted into an FDA cleared single use oxygen delivery device (GWR Medical, Inc. Chadds Ford, PA).
  - If necessary, a band around the wound is prepared for fixation of the Topical Oxygen device by shaving the limb circumferentially over approximately a 10cm band (done at initial treatment and as needed subsequently).
  - After the 90 minutes, the single use device will be removed and disposed of.
    - Wounds will be treated with standard care at the physician's discretion and diabetic foot ulcers (DFUs) will be administered with a standardized offloading boot to distribute pressure across the entire surface of the foot, specifically removing pressure from the ulcer site per SoC (a non-antimicrobial boot).

2. Trained study personnel will be assigned for the subject, who will receive at home support for the treatment. The study personnel will make weekly phone calls to the subject to check on progress with TO therapy; personnel may go to the subject's home/ care facility on as as-needed basis if the subject is having difficulty with the treatment.
3. Subjects will be given a data collection log (diary) to document the date, time and that the treatment was completed. This will be checked at each study visit and will be collected at their next follow-up visit for compliance.
4. Treatments will continue until the ulcer has closed, an amputation (above or below knee) has been performed, the ulcer's healing has stalled (defined that the size of the wound is unchanged or increased in size in the past 2 visits) or 16 weeks of therapy has been completed.

d. **SoC group only-** Patients will receive Standard of Care for their wound per the study physician's discretion. There will be no at home treatments for this study population but they will be asked to return for follow-up visits at 4, 8, 12, and 16 weeks following their baseline visit.

1. Subjects will be given a data collection log (diary) to document information about the SoC including wound dressing intact, offloading boot being used (for DFU's), the date, and the subject's initials. This will be checked at each study visit and will be collected at their next follow-up visit for compliance.
2. SoC will continue until the ulcer has closed, an amputation (above or below knee) has been performed, or the ulcer's healing has stalled (defined that the size of the wound is unchanged or increased in size in the past 2 visits).

All wounds for both groups will be treated with standard care and will be administered with a standardized offloading boot that distributes the pressure across the entire surface of the foot, specifically removing pressure from the ulcer site will be utilized (a non-antimicrobial boot). Offloading boots are standard of care for these wounds and will not be provided by the study.

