## **Objective:**

To observe the effect of application of topically administered oxygen on risk adjusted

outcomes (healing rates, rate of amputations, post-treatment health complications, cost of care) in 40 diabetic patients with chronic wounds.

This is a pilot study which is intended to collect data to calculate an adequate sample size for a larger registered clinical trial. Eleven subjects were enrolled at The Ohio State University; we intend to enroll 29 more subjects at Indiana University. Due to the small sample size this study will primarily be a feasibility study that will attempt to measure and evaluate differences in the relative theoretical costs of the intervention of topical oxygen therapy on this population and subsequently compare outcomes in areas such as overall health improvements and cost effectiveness.

Primary Outcome: Wound healing rates 16 weeks post treatment as compared to the baseline visit.

Secondary Outcomes: Rate of amputations, post-treatment wound complications such as wound infection, QoL (SF-36), cost of care 16 weeks post treatment as compared to the baseline visit.

For details of outcomes see **STUDY ASSESSMENTS AND PROCEDURES**

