#### **STANDARD OF CARE THERAPY (SoC):**

At the Comprehensive Wound Center, standard of wound care adheres to Clinical Practice Guideline, based on Wound Healing Society recommendations. Standard of care procedures (SoC) are intended to optimize conditions for wound healing and to ensure that a subject's safety is not compromised by taking part in this clinical study. The following standard of care procedures are routinely applied to patients at the Wound Center regardless of the group allocation across the entire duration of his or her participation in the clinical study.

- Wound cleaning and irrigation with normal saline
- Wound Dressings changes (examples below):
  - Non-adhering contact layer: open-mesh primary wound contact layer comprised of cellulose

- acetate coated with a soft tack silicone.
- Non-Adhering gauze dressing: gauze is made of knitted cellulose acetate fabric mesh that is coated with petrolatum emulsion.
- Off-loading:
  - Total contact casts (TCC) represent the best offloading practices.
  - Total contact casts will be changed on a weekly basis, and as needed for large exudative type wounds, twice weekly. An alginate or foam dressing will be incorporated over the foot ulcer prior to application.
  - If the subject is unable to use TCC or has discontinued using TCC for any reason, the subject will be offloaded with a removable cast walker. The reason for not using or discontinuing use of TCC will be recorded.
- If infection is suspected, appropriate therapy should be initiated according to the local therapy guidelines.
- **Group 2** will receive standard of care treatment plus Topical Oxygen Therapy. The provider will continue routine Standard of Care (SOC) that began prior to Topical Oxygen (TO) Therapy. Any changes in SOC will be based upon clinical practice guidelines and at the providers' discretion. [SOC changes will be documented by the research team to be considered during data analysis.]
  - The therapy will be applied in an identical manner utilizing the Topical Oxygen (TO) delivery device (FDA class II device) manufactured by GWR Medical Inc., and will be connected to an oxygen generator/concentrator. The devices maintain a constant pressure of 1.03 ATM which is just slightly above atmospheric pressure and much less than the typical 2.5 ATM used in hyperbaric oxygen (HBO) chambers.
  - All TO treatments will be provided in a home care or extended care (i.e. nursing home) setting.

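### The SoC-group procedures end standard care when a control ulcer stalls, which contradicts the protocol's own rule that standard care runs throughout participation in both groups

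*Combined protocol and SAP*

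**What the plan says.** Four statements bear on when SoC ends. All are in the protocol part of the combined document.

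- **Study Procedure, d. SoC group only, item 2:** "SoC will continue until the ulcer has closed, an amputation (above or below knee) has been performed, or the ulcer's healing has stalled". Stall is the third stopping event, and SoC itself is what stops.
- **Standard of Care Therapy, opening paragraph:** the SoC procedures (cleaning, dressings, off-loading, treatment of infection) apply "regardless of the group allocation across the entire duration of his or her participation in the clinical study". Part of their stated purpose is "to ensure that a subject's safety is not compromised by taking part in this clinical study". For Group 2 the section adds: "The provider will continue routine Standard of Care (SOC) that began prior to Topical Oxygen (TO) Therapy".
- **Study Procedure, d. SoC group only, closing paragraph:** "All wounds for both groups will be treated with standard care". It makes no exception for stalled wounds.
- **Study Procedure, c, item 4:** treatments stop at closure, amputation, stall or 16 weeks. The heading over this item is "At Home Treatments (4 consecutive days per week, treatment group only".

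Parts c and d define stall in the same way: "the ulcer's healing has stalled (defined that the size of the wound is unchanged or increased in size in the past 2 visits".

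The primary outcome is "Wound healing rates 16 weeks post treatment as compared to the baseline visit". Follow-up visits are at weeks 4, 8, 12 and 16.

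**The concern.** A coordinator with a stalled control ulcer cannot follow item 2 of part d together with the Standard of Care Therapy section and the closing paragraph of part d. Item 2 ends standard care and the other two continue it. Item 2 names nothing to take its place.

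Three things are at stake if item 2 is followed.

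- **Safety.** An open diabetic ulcer that is not healing could lose its dressings and off-loading because of a study instruction. The protocol says SoC is there to prevent that kind of harm.
- **The comparison.** The Study design and Statistical analysis sections compare TO+SoC with SoC. A control group in which the poorest healers stop SoC partway is a different comparator, and the lost weeks fall inside the outcome window.
- **Cost of care.** Costs are taken from the wound center's SoC billing, so control costs would be cut short in stalled wounds.

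The pilot is meant to supply estimates for a larger trial, so an unclear control condition would carry forward into that design.

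**Working it through.** The point is mainly textual. Arithmetic enters only for timing.

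**The plan's own figure.** The nearest figure is the power statement: 20 per arm, 50% against 10%, one-sided Fisher's exact test at 0.05, at least 80% power. Summing the two binomial distributions over all outcomes with p ≤ 0.05 gives 83.7%, so the statement is correct. The stall rule does not enter it, and this point does not dispute it.

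**What stops at a stall, by section**

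| Source | Control group | TO group |
|---|---|---|
| Standard of Care Therapy | SoC continues | SoC continues |
| Part d, closing paragraph | SoC continues | SoC continues |
| Part c, item 4 | does not apply | home treatments (oxygen) stop |
| Part d, item 2 | SoC stops | does not apply |

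Only the last row conflicts with the others. The two stopping rules share three stopping events and the stall definition, but item 2 of part d lacks the 16-week limit. This fits text carried over from part c without adaptation.

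**When SoC could first stop.** The stall definition does not say which visits are compared. Three readings are possible:

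- A: not smaller than at the previous visit. The first possible stop is week 4 (against baseline), leaving 16 − 4 = 12 weeks (75% of the window).
- B: not smaller at each of two successive visits. The first possible stop is week 8, leaving 16 − 8 = 8 weeks (50%).
- C: not smaller than two visits earlier. The first possible stop is again week 8, leaving 8 weeks (50%).

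A wound of exactly constant measured area would stop at 4, 8 and 8 weeks under A, B and C.

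**How much SoC a static control wound would get if item 2 is followed.** Assume no true change in area, visits on schedule, and continuous, independent, identically distributed measurement error. All 4! = 24 orderings of the areas at weeks 0, 4, 8 and 12 are then equally likely. A stall found at week 16 removes no SoC within the window.

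| Reading | Stop at week 4 / 8 / 12 / none (of 24) | Mean weeks of SoC |
|---|---|---|
| A | 12 / 8 / 3 / 1 | (48 + 64 + 36 + 16)/24 = 164/24 = 6.83 |
| B | 0 / 4 / 3 / 17 | (32 + 36 + 272)/24 = 340/24 = 14.17 |
| C | 0 / 12 / 6 / 6 | (96 + 72 + 96)/24 = 264/24 = 11.00 |

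As shares of 16 weeks these are 43%, 89% and 69%. They describe exposure to SoC under a literal reading of item 2. They say nothing about healing, because the documents give no information on how closure depends on weeks of SoC.

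**The case against.** The strongest reply is that nobody would follow item 2. SoC is given by the patients' own providers as routine wound care, part d opens by leaving care to the physician's discretion, and two other statements say SoC continues. On this view it is a drafting slip with no consequence in practice. The slip is likely, and the harm arises only if item 2 is followed. But the protocol still contains a written instruction to stop care in non-healing ulcers, and no other text overrides it.

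A second reply is that the asymmetry between groups is inferred. No sentence says outright that a stalled TO patient loses only oxygen; that rests on the heading of part c and on the Standard of Care Therapy section. One could read the two rules as parallel, each ending the assigned regimen. That reading is less natural. It would also make the conflict worse, because SoC would then stop in both groups against a section that continues it in both.

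A reader might go further and infer any of the following. The documents support none of them.

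- **That control patients have had care withdrawn.** Nothing shows which instruction staff follow.
- **That the trial is biased towards TO by a known amount.** The protocol does not say what care follows a stop. If the physician substitutes another treatment, control healing could rise. Any odds ratio would rest on an invented share of lost closures.
- **That stalled patients leave follow-up.** Part d asks controls to return at weeks 4, 8, 12 and 16, and the study timeline and week-16 section imply a final visit for all.

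**Conclusion.** The contradiction is real, stands in current text, and should be corrected. Item 2 of part d cannot be reconciled with the Standard of Care Therapy section or with the closing paragraph of part d.

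Its consequence is conditional. Under item 2, SoC could end as early as week 4 (reading A) or week 8 (readings B and C) at nominal visit dates, inside the 16-week window. That would be a safety problem and a departure from the planned comparison, probably in favour of TO. The size of any effect on healing cannot be derived from the documents, and the direction is open if another treatment is substituted. Under the Standard of Care Therapy section there is no bias, and the correction only removes a conflicting care instruction.

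The unclear stall definition does not carry this point by itself. Once stall no longer ends SoC, it affects only how long a non-healing TO wound receives oxygen, and the diaries record the sessions completed.

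**What to change.** 1. Delete item 2 of part d, or replace it with: *SoC continues for the entire duration of participation in both groups, as stated under Standard of Care Therapy; stalled healing does not end SoC or study follow-up in either group.* Removing only the stall clause would not be enough. Item 2 would still end SoC at closure or amputation, while the Standard of Care Therapy section continues it throughout participation, and early healers stay in the study to week 16.
2. In part c, item 4, state that stall ends topical oxygen only.
3. Optional clarification: say which visits the stall definition compares. The choice among the readings is the sponsor's.

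The cost is two wording changes, plus one more if the definition is clarified. No visits, data or study treatment are added, because SoC is already the patients' routine care.
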